9.3 Other study parameters

In the economic evaluation, primary aim will be to estimate the societal costs of the surgical strategy with a DAIR on day 10, and compare this to the costs of the nonsurgical treatment strategy. Secondary aim will be to estimate the cost effectiveness of the surgical strategy compared to nonsurgical treatment (from a societal perspective), based on the primary measure of effectiveness (number of infections prevented). Finally, a costs utility analysis will be performed based on EuroQol (5D-5L)-defined utilities.

Results of the cost effectiveness analysis will display the additional costs or savings with the surgical strategy in order to prevent one additional patient with an infection compared to nonsurgical treatment. Results of the cost utility analysis will display the additional costs or savings with the surgical strategy in order to gain one quality-adjusted life year (QALY) compared to nonsurgical treatment.

The time horizon of this study will be 12 months, therefore the analysis will not include discounting of costs and effects. Bootstrap resampling will be performed on the cost, and on the cost and effect pairs in order to calculate confidence intervals. Cost effectiveness acceptability curves will also be plotted, to estimate the probability of the surgical strategy being more cost-effective than the nonsurgical treatment strategy, for different amounts of money that a decision-maker may be willing to pay for one additional unit of effect (infection avoided, QALY).

BUDGET IMPACT ANALYSIS (BIA)

General considerations

A budget impact analysis will be conducted from a healthcare perspective as well as from a health insurance perspective. The basic case scenario will focus on a one-year impact at the national level. Scenario analysis will adopt a four-year horizon.

Cost analysis

A budget impact analysis (BIA) will be conducted to inform decision-makers about the financial consequences of the adoption and diffusion of the surgical strategy (DAIR) in

the Dutch healthcare system. The BIA will use a deterministic model. The model input parameters will be mainly based on results of the current clinical- and cost-effectiveness study and available literature. For the BIA, no additional patient level data will be collected.

The analyses will be conducted from various perspectives, including a direct medical perspective, a government and societal budgetary care perspective (overheidsperspectief), a budgetary care perspective limited to net bKZ expenditures (“netto bKZ-uitgaven”), and a health insurer’s perspective. For the analysis from a direct medical perspective, only costs within the healthcare sector will be taken into account. Unit prices will be based on Dutch standard prices (2015 guidelines). For the other perspectives, national tariffs will be applied (NZa tariffs) and the scope of included costs will be limited to those relevant for the perspective concerned. The precision of costs will be in accordance with the described perspectives (€M).

The model will take into account changes in the availability and adoption of the surgical strategy by calculating the financial consequences of the following scenarios:

- Situation in which all patients receive the nonsurgical treatment strategy.
- Situation in which all patients receive the surgical strategy.
- Situation in which all patients are treated gradually according to the study protocol (DAIR).
- Situation in which treatment according to the study protocol (DAIR) is considered suitable and available for varying percentages of the targeted population.

For each of the presented scenarios, a time horizon of up to four years will be applied. Alternative time horizons will be addressed in sensitivity analyses. Costs will be calculated based on changes in resource use, valued against the price level relevant from the various perspectives. Discounting of future costs will not be applied in the BIA.

The model will allow additional analyses for subgroups of patients. These analyses include mainly the shift in the subgroups of patients based on indication, type of surgery, age, BMI, ASA, medication groups (anticoagulants, immunosuppressants) and comorbidity (e.g. diabetes). Budget information for relevant subgroups will be made available for decision-makers. The planned sensitivity analysis will address the main input parameters and assumptions of the model, and financial consequences of variations in model parameters will be calculated for each of the applied perspectives [Mauskopf, 2007].

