Thus, prolonged wound leakage can be interpreted as a sign of prosthetic joint infection, but according to other authors it may also be seen as a risk factor for a deep infection, since a leaking wound can be a *porte-d-entrée* for bacteria. The latter is explained by the retrograde infection pathway described by Weiss and Krackow 1993, i.e. a leaking wound can be a pathway for bacterial colonisation. Persistent wound drainage can therefore be seen as risk factor for infection or as potential imminent infection, with fluid production as reaction on the infectious process. The latter perspective would have a low threshold for performing surgical debridement and lavage [Vince 2007, Ghanem 2014]. Irrespective of the treatment modality chosen, consensus states that early adequate treatment should be started as soon as possible if a PJI is suspected [Vince 2007, Lonner 1999, Maathuis 2009, Jaber 2008, Patel 2007, Saleh 2002, Ghanem 2014]. The treatment strategies toward wound leakage vary from non-surgical treatment (bed rest, pressure bandage, wound care) to surgical treatment (DAIR). In fact, nonsurgical treatment is aimed at stopping wound leakage and DAIR is aimed at treating deep wound infection.

DAIR is meant to clean the prosthesis and the wound, and eradicate biofilm in order to conquer the infection and escape revision surgery for infection. Bacteria attached to the implant encapsulate themselves in a slime layer (biofilm), invisible to the body's innate immune response and out of reach of antibiotics [Busscher 2013]. Antibiotics do not reach the bacteria in biofilm state and only work in combination with surgery. DAIR carries a risk (probably 1-2%) of causing a new infection; it requires anaesthesia and therefore patients are subject to the regular complication risks of surgery like anaesthesia-related problems and nerve or vascular injury. It is also hypothesized that DAIR is likely executed unnecessary, as the optimal timing for a DAIR has not been proven yet. Maybe if one waits longer, the wound will heal without surgical intervention. It is generally assumed that biofilm matures within two weeks, and a mature biofilm is more difficult to eradicate. Hence theoretically, if one aims at

removing a biofilm it is best done within this term. Every intervention at an early stage is aimed at preventing major revision surgery for PJI in the future, avoiding unnecessary interventions.

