7. METHODS

7.1 Study parameters/endpoints

7.1.1 Main study parameter/endpoint

The primary clinical outcome is the percentage of prevented revision for PJI within one year and the involved costs.

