7.1.3 Other study parameters (if applicable)

COST-EFFECTIVENESS ANALYSIS (CEA):

The cost effectiveness analysis typically integrates two quantities: 1. the additional costs (or savings) of the surgical protocol (DAIR) compared with the nonsurgical treatment, and 2. the additional health benefits. Based on these 2, a third metric is calculated: The Incremental Cost Effectiveness Ratio (ICER), which is the difference in costs, divided by the difference in effects.

Cost analysis

In the CEA, costs will include primary treatment (including home care) and health care associated with revision for infection in the first year (estimated from patient charts). Productivity losses will also be included. All items of resource use will be collected at the patient level, using CRFs and patient Questionnaires (iMCQ and iPCQ (www.imta.nl)). Estimated productivity costs will include short-term losses due to hospitalization and lifelong losses due to mortality (using general Dutch labor participation and income data). Health care will be valued using standard prices [zorginstituut Nederland, 2015], with time and travel costs included in the CUA. Productivity losses will be valued using both the friction-cost method (primary analysis) and the human-capital method.

Patient outcome analysis

In the CEA, patient outcome will be measured by the incidence of revision for infection. In the CUA, in the trial-based analysis the impact on QALY loss will rely on trial results based on the EQ-5D-5L. The quality of life assessments in our own patients will be used to calibrate the literature estimates to our specific patient population.

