9.1 Primary study parameter(s)

Clinical outcome

This study is designed as a randomized controlled trial. Every patient can be classified as nonsurgical or surgical. At least two measurements will be collected, namely before the

intervention (at day 9) and one year after the intervention. Between these two measurements additional information on the patient will be collected. The patient is also nested within a hospital, but the dependency of the measurements within the patient is our focal interest. The primary outcome of the study is revision surgery for PJI within one year (a binary variable). To take into account all these dependencies, multilevel logistic regression model with three levels will be used to analyse the data. The three levels are hospitals, patients and measurements, where measurements are nested within patients and patients are nested within hospitals. The effect of the intervention will be controlled with covariates such as age and gender.

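### Section 9.3 counts infections prevented as the cost-effectiveness effect and calls this the primary measure, while section 7.1.3 counts revisions for infection and the primary outcome is revision for PJI

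*Protocol*

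**What the plan says.** Section 7.1.3 defines the effect side of the cost-effectiveness analysis: "In the CEA, patient outcome will be measured by the incidence of revision for infection".

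Section 9.3 describes the same analysis with a different effect, in three places:

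- the aim is "based on the primary measure of effectiveness (number of infections prevented";
- the result is to be shown as the added cost or saving "in order to prevent one additional patient with an infection compared to nonsurgical treatment";
- the acceptability curve uses willingness to pay for "one additional unit of effect (infection avoided, QALY".

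The primary outcome is set in section 7.1.1 ("The primary clinical outcome is the percentage of prevented revision for PJI within one year and the involved costs") and again in section 9.1 ("The primary outcome of the study is revision surgery for PJI within one year (a binary variable"). The Summary and the research question also name revision surgery for PJI up to one year as the primary endpoint. The endpoint lists in sections 7.1.1 and 7.1.2 contain no infection-incidence endpoint. The nearest item is culture results, and the protocol has no rule for turning cultures into a count of infections.

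**The concern.** Two sections give different denominators for one ratio, and section 9.3 attaches the label of primary effectiveness measure to the one that is not the primary outcome. An analyst who follows section 9.3 literally divides the cost difference by infections avoided. One who follows section 7.1.3 divides it by revisions avoided. The two agree only if infection without revision is equally frequent in both arms.

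That equality cannot be presumed here, for three reasons:

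- **Purpose of DAIR.** Section 1 says it is meant to "eradicate biofilm in order to conquer the infection and escape revision surgery for infection". An infection that does not end in revision is therefore a result the surgical strategy aims for.
- **Risk from DAIR.** Section 1 also says that "DAIR carries a risk (probably 1-2%) of causing a new infection; it requires anaesthesia".
- **Detection.** Sections 4 and 7.3 call for one deep fluid culture and at least four tissue cultures at DAIR, which the whole surgical arm is assigned to have on day 10. Controls are advised to have DAIR only if still leaking at day 16. Otherwise their day 16 check is wound class, examination and CRP. An infection count would thus be looked for harder in one arm than in the other.

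If the conflict stays, the choice of denominator can be made after the data are seen.

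**Working it through.** **Which outcome the trial is built on.** The sample size in section 3.4 is for revision: 20% in controls and a 50% reduction, so 10% under DAIR, with 80% power and 0.05 (one-tailed according to section 9). With unpooled variance, n per group = (1.645 + 0.842)² × (0.20 × 0.80 + 0.10 × 0.90) / 0.10² = 154.6, rounded up to 155 as stated. Then 155 / 0.80 = 193.75, rounded up to 194 as stated. The planned size reproduces.

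**Effect of the unit on the ratio.** Let uS and uN be the infections without revision per 100 patients in the surgical and nonsurgical arms.

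- Revisions avoided per 100 = 20 − 10 = 10.
- Infections avoided per 100 = (20 + uN) − (10 + uS) = 10 + uN − uS.
- For the same cost difference, the ratio per infection divided by the ratio per revision is 10 / (10 + uN − uS).

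The 20%, 10% and 1-2% are the protocol's figures. How unrevised infections fall between the arms is assumed throughout.

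| Case | uS | uN | Infections avoided per 100 | Factor |
|---|---|---|---|---|
| Unrevised infections equal in both arms, or all DAIR-caused infections revised and so counted under both units | equal | equal | 10 | 1.00 |
| 1% DAIR-caused, unrevised; none in controls | 1 | 0 | 9 | 1.11 |
| 2% DAIR-caused, unrevised; none in controls | 2 | 0 | 8 | 1.25 |
| 1%, and half of controls have DAIR on days 17-20 at the same risk | 1 | 0.5 | 9.5 | 1.05 |
| 2%, and half of controls have DAIR on days 17-20 at the same risk | 2 | 1 | 9 | 1.11 |
| 5 per 100 unrevised, surgical arm only | 5 | 0 | 5 | 2.0 |
| 5 per 100 unrevised, nonsurgical arm only | 0 | 5 | 15 | 0.67 |

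**At the planned size.** With 155 per arm, 31 versus 15.5 revisions are expected, so 15.5 are avoided. Subtracting 1.55 (1%) leaves 13.95 infections avoided, and subtracting 3.1 (2%) leaves 12.4. Then 15.5 / 13.95 = 1.11 and 15.5 / 12.4 = 1.25, as in the table.

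**The case against.** The strongest reply is that section 9.3 uses infection as shorthand for revision for infection. It refers back to a primary measure that is defined elsewhere as revision. Section 7.1.3 counts the costs of revision for infection in the first year, so both sides of the ratio rest on revision. Section 3.4 presents the halving of revisions as following from the halving of PJI. With no definition of infection as an outcome, an analyst has only one defined endpoint that fits the label.

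This reading is plausible and may well be what was meant, but it does not settle the matter. The protocol nowhere states it, and section 9.3 uses the infection unit three times. Section 3.4 names two events joined by a causal step, and equal proportional reductions do not make the units equal. Suppose 25% of controls had PJI and 20% were revised (assumed). Halving both would avoid 12.5 infections but 10 revisions per 100, a factor of 10 / 12.5 = 0.8.

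The second objection is that the factors are driven by assumptions, run in both directions and include no effect. That stands. They show what the choice of unit can do and are not an estimate of bias.

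The Summary's 2% PJI against 0.4% revised within one year should not be used as evidence of unrevised infections. The 2% has no time window, and section 1 puts most revisions for PJI after the first year (about 800 of roughly 1064), so timing alone could explain the gap.

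**Conclusion.** The concern holds as a minor one. Sections 7.1.3 and 9.3 set different effect measures for the same analysis, and section 9.3 misnames infections prevented as the primary measure of effectiveness. Both statements rest on the text alone.

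The size is conditional. The factor on the ratio is 1.11-1.25 if the protocol's 1-2% of DAIR-caused infections go unrevised and controls have no unrevised infections, and 1.05-1.11 if half of controls also have DAIR. It is 1.00 if unrevised infection is balanced, and 0.67 or 2.0 with an assumed 5 per 100 in one arm only.

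The reach is the cost-effectiveness ratio and its acceptability curve, which section 9.3 ranks as the secondary aim of the economic evaluation. The primary clinical test, the sample size, the cost comparison and the cost-utility analysis do not change.

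**What to change.** In section 9.3, replace the infection unit by revision for PJI within one year in all three places: the aim, the displayed result and the acceptability curve. The section then agrees with sections 7.1.1, 7.1.3 and 9.1. If a ratio per infection avoided is also wanted, keep it as a labelled sensitivity analysis with one definition of infection applied to both arms.

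The main change costs three wording edits and needs no new data, patients or visits. Its drawback is that infections treated with the implant kept will show only in costs and QALYs, and not in the ratio per revision avoided.

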9.4 Interim analysis (if applicable)

NA

10. ETHICAL CONSIDERATIONS

10.1 Regulation statement

The study will be conducted according to the principles of the Declaration of Helsinki (Declaration of Helsinki, Brazil, October 2013) and in accordance with the Medical Research Involving Human Subjects Act (WMO) and other guidelines, regulations and Acts.

10.2 Recruitment and consent

All patients aged 18 or older and scheduled to undergo TKA/THA surgery in the participating hospitals will be orally informed about the LEAK study by their physician or specialised nurse when he or she is placed on the planning list for TKA/THA. In addition the patient will receive written information in the form of a flyer with background information about the study.

At the day of hospitalization all TKA/THA patients will be informed again about the study orally by the independent local research physician/nurse. On day 5-7, in case of persisting wound leakage, patients will receive a patient information letter and oral information by an independent research physician/nurse about the study and they will be asked to think about participating.

On day 9-10, patients can communicate their final decision (yes or no) to the local independent research physician/nurse with respect to participation in the study. If patients agree to participate, written informed consent will be obtained.

In case their wound is still leaking at day 9-10, they will be randomized to nonsurgical or surgical treatment.

In case the wound is dry at day 9-10, or if patients have to undergo DAIR because of high clinical suspicion for infection ($T > 38.5$, red indurated wound and pain), patients are not eligible to randomization but they can give permission to use their data for comparative analyses.

For the sake of facilitating logistics in the participating centres, consent and randomization are set at day 9 or 10; DAIR is set at day 10-11. In the general text, for easy reading, these terms are simplified to day 9 and day 10 respectively.

10.3 Objection by minors or incapacitated subjects (if applicable)

In case of incapacitated subjects, the subject will not be asked to participate.

10.4 Benefits and risks assessment, group relatedness

The goal of the study is to compare two standard clinical policies, which are currently both used as usual care in the Netherlands depending on the physician's or hospital's preference. The patients in our trial will be subjected to one of these standard policies. It is therefore plausible that participation will lead not to an increased health risk. The burden of participation in the trial can be considered minimal as treatment regimens within the study are in line with usual care strategies. No extra hospital visits are required.

10.5 Compensation for injury

Aangezien het onderzoek een vergelijking betreft van in Nederland gebruikelijke behandelingen op het gebied van de geneeskunst heeft de oordelend commissie, de METc UMCG, ontheffing van de verzekeringsplicht verleend zoals bedoeld in art. 4 lid 2 van het Besluit verplichte verzekering bij medisch wetenschappelijk onderzoek met mensen.

10.6 Incentives (if applicable)

NA

11. ADMINISTRATIVE ASPECTS, MONITORING AND PUBLICATION

11.1 Handling and storage of data and documents

Personal data will be handled confidentially. Every subject will receive a unique code, this code contains the number of the hospital (UMCG/ HAGA Ziekenhuis, Onze Lieve Vrouwe Gasthuis etc.) followed by the number corresponding with the study group (nonsurgical/surgical). This combination of three numbers will be supplemented with a unique sequence number. Data of each subject will be collected under this unique code. A unique subject identification list will be used to link the data to the subject. The key to the code is safeguarded by the coordinating investigator. All source documents will be entered in an electronic CRF.

11.2 Monitoring and Quality Assurance

Based on the negligible risk profile, minimal monitoring is considered adequate (according to the NFU standards). Monitoring digitally will be performed for critical data (e.g. completeness of questionnaires) and will be executed by an independent subject of the orthopaedic department, not related with the study, with relevant training and education.

11.3 Amendments

Amendments are changes made to the research after a favourable opinion by the accredited METC has been given. All amendments will be notified to the METC that gave a favourable opinion.

11.4 Annual progress report

The sponsor/investigator will submit a summary of the progress of the trial to the accredited METC once a year. Information will be provided on the date of inclusion of the first subject, numbers of subjects included and numbers of subjects that have completed the trial, serious adverse events/ serious adverse reactions, other problems, and amendments.

11.5 Temporary halt and (prematurely) end of study report

The investigator/sponsor will notify the accredited METC of the end of the study within a period of 8 weeks. The end of the study is defined as the last patient's last visit.

The sponsor will notify the METC immediately of a temporary halt of the study, including the reason of such an action.

In case the study is ended prematurely, the sponsor will notify the accredited METC within 15 days, including the reasons for the premature termination.

Within one year after the end of the study, the investigator/sponsor will submit a final study report with the results of the study, including any publications/abstracts of the study, to the accredited METC.

11.6 Public disclosure and publication policy

The present study is investigator initiated. No arrangements are made between the subsidizing party and investigator concerning publication of the research data. Independent of the outcome, the results of the study will be published in international peer-reviewed scientific journals. Patient data will be presented anonymously in all publications and scientific journals. This prospective clinical trial will be registered in the "Nederlands Trial Register" before the first patient is recruited.

12. STRUCTURED RISK ANALYSIS

NA

